2.2 Analysis sets

The **Full Analysis Set (FAS)** includes all patients who received at least one dose of eltrombopag.

The **Safety Set** includes all patients who received at least one dose of eltrombopag.

2.2.1 Subgroup of interest

For the final CSR, , selected outputs will be presented by SRoT status, e.g. data will be displayed by “SRoT until M12”, “non-SRoT untilM12” and “All patients”. “SRoT untilM12” patients are patients who met the primary endpoint definition (all four steps until Month 12). Additionally, the primary efficacy outputs will be presented by the time since ITP diagnosis.

2.3 Patient disposition, demographics and other baseline characteristics

The Full Analysis Set (FAS) will be used for all baseline and demographic summaries and listings unless otherwise specified.

2.3.1 Patient disposition

Disposition data will be summarized descriptively and listed. Summaries will include all reasons for treatment or study discontinuation as reported on the disposition eCRF pages. Number (%) of patients who permanently discontinued study treatment with reason, as reported in the dose administration record eCRF pages will also be provided.

Informed consent and inclusion/exclusion criteria data will also be listed.

Data will be listed for screening failures.

2.3.2 Patient demographics and other baseline characteristics

Country specific regulations should be considered for the collection of demographic and baseline characteristics in alignment with CRF

The following patient demographics and baseline characteristics will be collected on the eCRF:

- Demography including age, sex, predominant race and ethnicity (where permitted)
- Height and weight
- Medical history (e.g., important medical, surgical, and allergic conditions from the patient’s medical history which could have an impact on the patient’s evaluation)/ current medical conditions (e.g., all relevant current medical conditions which are present at the time of signing informed consent). Ongoing medical conditions, symptoms and diseases which are recorded on the Medical History eCRF should include the toxicity grade when applicable
- Prior and concomitant medications

Bone marrow biopsy is optional and recommended for patients who did not respond to steroids and are considered refractory. It can be performed during treatment at the discretion of the investigator.

All assessments to be completed and documented during screening are detailed in Table 8-1 of the study protocol.

Demographic and other baseline data including disease characteristics will be listed and summarized descriptively based on the FAS. Age will be summarized descriptively and will also be categorized in the following intervals: 18-<45 years, 45-<65 years, 65-<75 years, 75-<85, >=85 years.

Time since initial diagnosis (days) = First dose date-date of initial diagnosis, will be summarized descriptively based on the FAS.

Relevant medical histories and current medical conditions at baseline will be summarized by system organ class and preferred term.

2.4 Treatments (study treatment, rescue medication, concomitant therapies, compliance)

2.4.1 Study treatment / compliance

The number of patients with dose adjustments (reductions, interruption, or permanent discontinuation) and the reasons will be summarized and all dosing data will be listed.

The duration of exposure in months to eltrombopag will be summarized descriptively and will also be categorized in the following intervals: <3 months, 3-<6 months, 6-<9 months, 9-<12 and >=12 months, and less than 1 Month, at least 1 month, at least 2 months, and so on. The duration of exposure excluding days of zero dose will be summarized with the same categorization. The dose intensity and the relative dose intensity will be summarized by means of descriptive statistics. Mean, SD, median, maximum, minimum, 25th percentile and 75th percentile will be provided. Relative dose intensity will also be categorized in the following intervals: <75%, 75-<=90%, 90-<=110%, >110%.

2.4.2 Rescue therapy

Any ITP-directed medication or therapy, other than eltrombopag, given during the trial with the aim to increase platelet count for the patients who have clinically significant bleeding will be considered a rescue therapy and must be recorded on the appropriate CRF page (Form: Concomitant Medication, the category value at the form: Rescue medication). A patient who receives rescue medication or therapy between Step 2 and Step 3 will not be eligible for Step 3. A patient who receives rescue medication or therapy between Step 3 and Step 4 will not be eligible for Step 4. A patient who receives rescue medication or therapy will not be considered in having achieved sustained response off treatment for the primary endpoint, unless the patient uses steroids ± IVIG as described below in the first 14 days of start of eltrombopag.

Steroids ± IVIG use as rescue medication:

In case of clinical need such as very low platelet count (<10×10⁹/L) and/or significant bleeding, treatment with steroids ± IVIG and platelet transfusion is permitted together with eltrombopag for the first 14 days, calculated from the first dose day of eltrombopag. Any rescue therapy started before Day 14 may be used after Day 14 if the dose is considered low dose as per protocol definition and is being tapered down (i.e., successively lower doses after day 14).

Rescue medication will be taken from the SDTM cm.sas7bdat dataset where cmcat='RESCUE MED' for rescue therapy and exported as an EXCEL file. The clinical team will review the records captured in an Excel spreadsheet. Medications which were not considered as rescue therapy were flagged as 'Y' for the column 'NOT_RESCUE'. Per protocol, medications prior to Day 14 are not considered as rescue medication in the efficacy derivations and will be programmatically excluded. Medications that started prior to Day 14 and were still being tapered after Day 14 will also be programmatically excluded from efficacy derivations.

Once the database has locked the data will be rechecked again for any changes or new data that needs flagging.

The spreadsheet will contain patient level data with patient number (USUBJID), sequence number (CMSEQ), reported drug name (CMTRT), standardized medication name (CMDECOD), category for medication (CMCAT), indication (CMINDC), dose per administration (CMDOSE), dose units (CMDOSU), dosing frequency per interval (CMDOSFRQ), start date/time of medication (CMSTDTC), end date/time of medication (CMENDTC), indication 1(CMINDC1), indication 2 (CMINDC2), reported name of drug trade name (CMTRDNAM), not rescue medication flag (NOT_RESCUE).

The spreadsheet will be imported into the programming environment (GPS) and merged with the patient data for the analysis. The EXCEL document will be stored in CREDI in the study folder ETB115J2411/Administrative Files (study level)/RAP or RAMP Meeting and in GPS in the study folder: CETB115J2411\csr_1\util.

Platelet transfusions will be taken from the ADCM and ADPR datasets. The variables category for medication (CMCAT), standardized medication name (CMDECOD), reported name of drug, medication, or therapy (CMTRT) from the ADCM will be used for the looking for platelets transfusions. The CMCAT values should be equal to 'RESCUE MED', and CMDECOD and/or CMTRT should contain the text 'PLATELET'. The variables contained reported names of procedure (PRTRT) and standardized procedure name (PRDECOD) from ADPR will be used for the looking for platelets transfusions. The PRDECOD and/or PRTRT should contain the text 'PLATELET'.

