Prednisone	0.5–2 mg/kg/day, for 2–4 weeks until a response is seen, followed by tapering over several weeks	Initial response: 60–80% Sustained response: 20–47%	AEs vary with the dose and duration, but include weight gain, anxiety, insomnia, and diabetes
Dexamethasone	40 mg/day, for 4 days every 2–4 weeks, for 1–4 cycles	Initial response: up to 90% Sustained response: 40–50% Repeated cycles may result in response rates up to 80%	Weakness, insomnia, and impaired cognition
IVIG	0.4 g/kg/d for 5 days or 1 g/kg/d for 1–2 days	Initial response: up to 80% Platelet count usually returns to pretreatment levels within 2–4 weeks, persists for months in few patients	Common: headache, hypertension, and chills Rare: hemolysis and neutropenia
Anti-D	50–75 µg/kg	Similar to IVIG, dependent on dose	Common: hemolysis Rare: intravascular hemolysis, can be fatal

Source: [Provan 2010](#)

In general, 60-70% of adults with acute ITP achieve an initial response; even higher response rates are reported in children. Rates of sustained response with corticosteroid treatment (usually defined as a platelet count ≥ 50 or $\geq 100 \times 10^9/L$ at 6-12 months, with different timeline and platelet count thresholds within different publications) are generally low and vary from 20% to 47%. With longer follow-up, the risk of relapse increases in adults who experience an initial response.

Many of the currently available treatments, in particular, high doses of steroids, are associated with significant morbidity. Historical data has shown that mortality from ITP more often results from infectious complications of steroid treatment and splenectomy rather than directly from bleeding. Thus, there is an important need for a tolerable therapy for patients that do not experience early ITP remission with steroid treatment.

Options for salvage therapy include retreatment with corticosteroids, switching from one steroid type to another, a combination of first-line agent(s), or treatment with a second-line agent. According to current guidelines available modalities for second line treatment options for ITP patients have quite different mechanisms of action. They are broadly classified into those that are given only once (or for only one course) and are intended to induce long-term remission (splenectomy, rituximab) and those that need continued or chronic administration (corticosteroids, immunosuppressive agents and Thrombopoietin Receptor Agonists [TPO-RAs]).

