6.2.3 Rescue therapy

Any ITP-directed medication or therapy, other than eltrombopag, given during the trial with the aim to increase platelet count for the patients who have clinically significant bleeding will be considered a rescue therapy and must be recorded on the appropriate CRF page. A patient who receives rescue medication or therapy will not be considered in having achieved sustained remission for the primary endpoint, unless the patient uses steroids ± IVIG as described below in the first 14 days of start of eltrombopag.

Steroids ± IVIG use as rescue medication:

In case of clinical necessities because of very low platelet count ($< 10 \times 10^9/L$) and/or significant bleeding, treatment with steroids ± IVIG and platelet transfusion is permitted together with eltrombopag for the first 14 days, calculated from the first dose day of eltrombopag.

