2.5.2 Statistical hypothesis, model, and method of analysis

The number (%) of patients with sustained response off treatment by month 12 will be summarized together with 95% confidence interval (CI) using the Clopper-Pearson method.

A binomial test for one proportion, $H_0: P=0.15$ vs. $H_1: P>0.15$ will be performed to test if the proportion of sustained response off treatment patients is greater than 15% using a target alpha level of 0.05.

Listing for hematologic response, with flags for: platelets $<30 \times 10^9 / L$, bleeding events, transfusions, and rescue medications will be provided. Steps until sustained response off treatment at month 12 and during the follow-up period will be flagged as follows:

- Patients who reached platelet count $\geq 100 \times 10^9 / L$ at least once
- Patients who maintained stable platelet count for 2 months after reaching $100 \times 10^9 / L$ (no counts below $70 \times 10^9 / L$)
- Patients who were able to be tapered off the drug till treatment discontinuation, while maintain platelet count $\geq 30 \times 10^9 / L$ in the absence of bleeding (no bleeding AEs) or use of any rescue therapy
- Patients with sustained response off treatment until month 12, while maintain platelet count $\geq 30 \times 10^9 / L$ in the absence of bleeding (no bleeding AEs) or use of any rescue therapy
- Patients with sustained response off treatment from month 12 to month 24, while maintain platelet count $\geq 30 \times 10^9 / L$ in the absence of bleeding (no bleeding AEs) or use of any rescue therapy

The patients can re-attempt Steps 1 to 3.

The patient cannot be considered as having achieved SRoT (step 4) in the cases below:

1. If a patient has taken rescue med prior to day 14 and if the dosage was increased after day 14 they are not considered as Step 4 at month 12.
2. If a patient has taken new rescue med after day 14 they are not considered as Step 4 at month 12.
3. If a patient taken platelet transfusion after day 14 they are not considered as Step 4 at month 12.

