3.1.2 Responders cut-off update due to final sample size

For decision-making purposes, responders cut-off will be determined based on the final sample size and the target alpha and beta.

A final sample size of 105 gives at least 80% power if the true sustained response rate on eltrombopag is 25% or more with an actual significance level of **0.037**. The null hypothesis will be rejected if the number of responders is **23** or more (instead of 22 for an initial sample size of 101 patients as stated in Protocol, section 12.8.1).

[Table 3-2](#) shows the sample size, cut-off, actual alpha, beta and power for different sample sizes.

Table 3-2 **Numeric results for testing $H_0: P = P_0$ versus $H_1: P > P_0$ using exact binomial test statistic, for a sample size of 101 and 105 patients**

Sample size (N)	Proportion given H_0 (P_0)	Proportion given H_1 (P_1)	Cut-off (Reject H_0 if $R \geq$ This)	Actual Alpha	Actual Beta	Actual Power
101	0.150	0.250	22	0.043	0.196	0.804
105	0.150	0.250	23	0.037	0.200	0.800

4 Changes to protocol specified analyses

In Section 6.2.3 of the study protocol there is stated that a patient who receives rescue medication or therapy will not be considered in having achieved sustained response off treatment for the primary endpoint, unless the patient uses steroids \pm IVIG as described below in the first 14 days of start of eltrombopag. Steroids may be used after day 14 if the dose is considered low dose as per protocol definition and/or tapered down (i.e., successively lower doses after day 14). This change applies to the derivation of all efficacy endpoints.

By clinical practice, a patient can have a bleeding event during first 7 days after eltrombopag start. Only bleeding events that happen from day 8 onwards after the eltrombopag start will

exclude a patient to reach an efficacy endpoint. This change applies to the derivation of secondary efficacy endpoints 3, 4 and 6.

In addition to descriptive statistics, box plots will also be provided for FACIT, FACT-Th6 and SF-36 questionnaire scores.

The end of study (EOS) has been revised to end of treatment (EOT).

“Sustained remission” was changed to “sustained response off treatment”.

Starting dose for Asian patients and Japanese patients in Japan described.

Study objective and endpoints updated in accordance with clarifications of the protocol: described above.

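### SAP 2.4.2 drops all rescue medication given before Day 14 "per protocol", but protocol 6.2.3 and the SAP's own preceding paragraph exempt only steroids ± IVIG

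*SAP*

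**What the plan says.** Protocol 6.2.3 defines rescue broadly: "Any ITP-directed medication or therapy, other than eltrombopag, given during the trial with the aim to increase platelet count", in patients with clinically significant bleeding. A rescued patient has not achieved sustained remission for the primary endpoint "unless the patient uses steroids ± IVIG as described below in the first 14 days of start of eltrombopag". The next paragraph describes what may be given early: "treatment with steroids ± IVIG and platelet transfusion is permitted together with eltrombopag for the first 14 days", counted from the day of the first dose.

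SAP 2.4.2 repeats the broad definition and the steroids ± IVIG exemption almost word for word. Under a steroids ± IVIG subheading it then allows rescue begun before Day 14 to continue afterwards if it is low dose and being tapered. The programming instruction follows: "Per protocol, medications prior to Day 14 are not considered as rescue medication in the efficacy derivations and will be programmatically excluded". A further sentence also drops medications begun before Day 14 that are still being tapered after it.

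SAP 2.5.2 lists three things that block Step 4: a dose increase after Day 14 of rescue begun before Day 14, a platelet transfusion after Day 14, and new rescue, worded as "If a patient has taken new rescue med after day 14 they are not considered as Step 4 at month 12".

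SAP section 4 declares one departure from protocol 6.2.3: "Steroids may be used after day 14 if the dose is considered low dose as per protocol definition and/or tapered down". It applies this to all efficacy endpoints and mentions no other drug class.

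**The concern.** The sentence that will be programmed is looser than the rule it cites and looser than the rule stated earlier in the same section. It removes records by date alone, so an early dose of an ITP drug other than steroids or IVIG disappears from the derivation. Nothing downstream restores it: the Step 4 list looks only after Day 14, and the clinical team's NOT_RESCUE flag only takes records out.

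At stake is whether a patient whom the protocol scores as a failure can be counted as a success on the primary endpoint. Endpoint 3 (a count of at least 50 × 10⁹/L in month 1, without rescue) is also exposed, because Days 1 to 13 make up 13 of the roughly 30 days in its window. There, a platelet rise after another agent could be credited to eltrombopag.

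SAP section 1 says the primary CSR is final, but Month 12 response status carries forward. It defines the final-CSR subgroups (SAP 2.2.1) and the population for duration analysis 1b (SAP 2.7.2).

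**Working it through.** **1. One record under both rules.** Suppose anti-D, which protocol Table 1-1 lists as an ITP treatment, is given once on Day 5 for clinically significant bleeding.

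| Question | Protocol 6.2.3 | SAP 2.4.2 programming rule and 2.5.2 |
|---|---|---|
| Is it rescue? | Yes: ITP-directed and not eltrombopag | Record dropped: before Day 14 |
| Is it exempt? | No: neither steroid nor IVIG | Yes, by date |
| Dose increase, new rescue or transfusion after Day 14? | Not relevant | None |
| Primary endpoint | Non-responder | Can reach Step 4 if counts, taper and follow-up qualify |

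For endpoint 3 the dropped record leaves no rescue on file. The Day 5 bleed does not fail the patient either, because SAP 2.8.4.4 and section 4 disregard bleeding up to Day 7.

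**2. Day 14.** SAP 2.1.1 makes the first dose day Day 1, so the protocol's first 14 days are Days 1 to 14. SAP 2.4.2 excludes what is prior to Day 14, and SAP 2.5.2 penalises what is new after Day 14.
- A steroid started on Day 14 is exempt under the protocol but is not dropped by the SAP exclusion. A protocol success could become a failure.
- Another ITP drug started on Day 14 is rescue under the protocol but is not on the Step 4 list. A failure could become a success.

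**3. The plan's own test.** Inputs from SAP 2.5.2 and 3.1.2: N = 105, null rate 0.15, alternative 0.25, reject at 23 or more, one-sided target alpha 0.05. With X binomial:
- P(X ≥ 23 | 105, 0.15) = 0.0373; the SAP prints 0.037.
- P(X ≥ 23 | 105, 0.25) = 0.7995; the SAP prints 0.800.
- P(X ≥ 22 | 105, 0.15) = 0.0626, so 23 is the correct cut-off.

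The design figures reproduce, and the scoring question does not alter them.

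**4. Sensitivity to misclassification.** The observed p-value is 0.063 at 22/105 and 0.037 at 23/105. One patient adds 1/105 = 0.95 percentage points.

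Suppose k patients are certain to be wrongly scored as responders and the other 105 − k respond at 15%. The error is then P(X ≥ 23 − k | 105 − k, 0.15):

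| k | Error |
|---|---|
| 0 | 0.037 |
| 1 | 0.057 |
| 2 | 0.086 |

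**5. Exposure is not certainty.** A patient given such a drug must still meet every platelet and taper step. Let q be the chance that one exposed patient is scored a responder. The error is q × P(X ≥ 22 | 104) + (1 − q) × P(X ≥ 23 | 104) = q × 0.0573 + (1 − q) × 0.0338, both at 15%.
- q = 0.25 (illustrative): 0.040.
- q = 0.50 (illustrative): 0.046.
- It passes 0.05 only above q = (0.05 − 0.0338)/(0.0573 − 0.0338) ≈ 0.69.

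**The case against.** The strongest reply is that the section states the right rule. The programming sentence sits under a steroids ± IVIG subheading, after a paragraph giving the protocol limit, so its opening words can be read as pointing back to that limit. This makes the fault an internal contradiction, not a wholesale replacement of the protocol rule. It does not remove the fault, because the derivation instruction names no class and the same section speaks of any rescue therapy started before Day 14.

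Second, protocol 6.2.2 bars other ITP-directed therapy, and 9.1.1 requires study treatment to stop after prohibited treatment. A patient stopped that way has not tapered per protocol and cannot reach Step 3. This probably makes cases rare. It does not close the gap, because 6.2.2 defers to 6.2.3 for rescue and 6.2.3 defines rescue as any ITP-directed therapy.

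Three stronger readings are tempting but not supported:
- A reader might infer that anything started before Day 14 is ignored whatever follows, for example rituximab begun on Day 10 and repeated at the same dose. SAP 2.4.2 exempts continued use only when it is low dose and tapering, so that case fails the condition.
- A reader might infer that the rule can only turn failures into successes. The Day 14 gap can work the other way.
- A reader might lower the cut-off to 22 or 21 at N = 105 and quote errors of 6.3% and 10.0%. That keeps all 105 patients at the null rate and adds the false responders on top, implying 106 or 107 patients.

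**Conclusion.** The point holds as a contradiction within SAP 2.4.2 and between it and protocol 6.2.3, undeclared in section 4. As written, the derivation can score a protocol non-responder as a responder on the primary endpoint and on endpoint 3. Day 14 is unassigned, and the scoring of early platelet transfusion is unsettled: the protocol permits it in the first 14 days but does not name it in the scoring exemption.

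Actual bias is not shown. The number of patients given another ITP drug in the first 14 days is not in the documents and may be zero. The rise from 3.7% to 5.7% or 8.6% assumes that one or two such patients exist and are certain to be scored as responders; at a 25% to 50% chance, one exposed patient leaves the error at 4.0% to 4.6%. The case for acting is that a single patient separates rejection from non-rejection at the cut-off and the correction is cheap.

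**What to change.** These changes concern scoring only, not which rescue treatment is given.

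- In SAP 2.4.2, limit the early exclusion to the therapies that protocol 6.2.3 exempts from scoring (steroids ± IVIG). Identify them by standardised name or ATC class; CMDECOD is already in the review spreadsheet.
- Score any other ITP-directed medication from Day 1 as rescue.
- Keep the existing low-dose and taper condition for use after Day 14.
- Word the boundary as on or before Day 14 versus after Day 14, consistently in 2.4.2 and 2.5.2.
- Reconcile protocol 6.2.3, SAP 2.4.2 and SAP 2.5.2 on how platelet transfusion in the first 14 days is scored, and state the answer.

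If the reported primary derivation is to stand, declare the wider rule in section 4 and add a sensitivity analysis that scores other early ITP therapy as non-response. Report how many patients change status, even if none do.

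The cost is a short text change and a filter, plus either a small re-derivation of an endpoint already reported or one extra analysis. Sample size, cut-off and test are unaffected.
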